### **10.4.3 Overview of Treatment-Emergent Adverse Events Generating an Event of Special Interest**

An overview summary table of TEAEs generating an event of special interest will be prepared for the following categories:

- All AEs
- AEs leading to death
- Serious AEs
- Severe AEs (CTCAE grade 3-5)
- AEs leading to withdrawal

This table will be prepared for each AESI (cardiovascular event, bone fracture, and glucose intolerance).

### **10.4.4 Incidence of Adverse Events Generating an Event of Special Interest**

Summary tables will be prepared for the incidence of the treatment-emergent adverse events generating an event of special interest. The tables will be sorted by

- MedDRA SOC (alphabetically) and PT (in decreasing frequency of occurrence)
- MedDRA SMQ (in decreasing frequency of occurrence) and PT (in decreasing frequency of occurrence).

## 10.5 Analyses of Adverse Events of Special Interest

### 10.5.1 Primary Analysis of Adverse Events of Special Interest (AESI)

The mortality rate and respective incidence rates (number of AEs per 100 person years) of each AESI will be estimated using a Poisson regression model. In general, assuming a constant incidence rate of  $\lambda_{i,j}$  per unit time for a category  $i$ , treatment  $j$  ( $=0$  for GnRH agonist and 1 for Firmagon), the number of events  $y_{i,j}$  observed during a time interval of length  $t_{i,j}$  (unit 100 years) is distributed as Poisson with mean  $\mu_{i,j}=\lambda_{i,j}t_{i,j}$ . The mean of a Poisson distributed variable is modelled by

$$\log \mu_{i,j} = \log \lambda_{i,j} - \log t_{i,j} = \alpha + \beta_j + \beta_{i,j} x_{i,j},$$

where  $t_{i,j}$  is the number of person years, and  $\log(t_{i,j})$  is modelled as the “offset” with regression coefficient equal to one. Besides the effects of intercept ( $\alpha$ ) and treatment, modelled by  $\beta_j$  (with GnRH agonist as reference; e.g.  $\beta_0=0$ ), the incidence rate (mean) is driven by the adjusting factors for the present category. By this, the adjusted incidence rate ratio (IRR) of an incidence for patients on Firmagon as compared to GnRH agonist is estimated by  $\exp(\beta_i)$ . For more details, please see page 501 of [5], and page 204 of [6].

Table 5 illustrates data from one treatment arm by each category of adjusting factors (age and stage of disease) used in the model. This example may be extended to include more adjusting factors if required.

### **10.5.2 Time-to-First Event by Kaplan-Meier Methodology**

Comparisons between the two treatment arms with respect to time-to death, and time-to first event of special interest, will be based on the log-rank test using the Kaplan-Meier methodology.

Patients who are lost to follow-up before experiencing the adverse event of interest will be censored.

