#### 3.1 Schedule of Assessments

Patients will be enrolled after the initial decision (by the investigator) has been made to introduce Firmagon or GnRH agonist as per label indication for prostate cancer. Data will be collected at baseline and every 3 months ( $\pm$  4 weeks) for the first 2 years, then every 6 months ( $\pm$  6 weeks) for the remaining 3 years. Firmagon is dosed monthly, while GnRH agonists may be administered less frequently, therefore suggested data collection time points *may not always* coincide with treatment-related clinical visits. If necessary, telephone outreach may be used by sites to collect relevant data. Patients who discontinue ADT therapy will continue to be followed for safety outcomes in order to assess the long term safety associated with ADT.

A flowchart of *recommended* study assessments is provided in [Table 1](#).

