## **6 Analysis Dataset**

As the study is non-randomised the intention to treat principle (analyses according to the planned treatment regimen) will not be followed. All analyses will be performed on the actual (received) treatment.

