#### **10.1.1 Table Shell for Adverse Events**

To make a balanced comparison with respect to possible differences in drop-out rates, the standard safety table will display the total number (N) of patients exposed, the number of patients reporting an AE, the percentage of patients (%) with an AE, the number of person years, the incidence rate and its 95% CI. The exact uniformly most powerful unbiased test of equal incidence rates will be used to flag significant differences between the two treatment groups.

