### **10.5.3 Cox Proportional Hazards Model**

Hazard ratios between Firmagon and GnRH agonist (=reference) with respect to death, and (first) event of special interest will be estimated based on the Cox proportional hazard model, adjusted for potential confounding factors as described in Section 10.5.1. Model parameters will be deemed statistically significant assuming a two-sided alpha level of 0.05 based on Wald test for individual parameters.

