#### **10.6.5 Time-to-First Event by Kaplan-Meier Methodology**

Comparisons between the two treatment arms with respect to time-to first event of CV SAE will be based on the log-rank test using the Kaplan-Meier methodology. This analysis will be repeated for the CV SAE including death as endpoint, and in the subgroup of patients with prior CVD at baseline. In all, four analyses are planned.

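### In a non-randomised cohort, the adverse event flags (SAP 10.1.1) and the log-rank tests (10.5.2, 10.6.5) ignore the factors the SAP adjusts for elsewhere; the AE flags have no adjusted counterpart

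*SAP*

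**What the plan says.** **Design.** SAP section 6 begins "As the study is non-randomised the intention to treat principle" and then sets that principle aside in favour of analysis by treatment received. Section 3.1 has patients enrolled "after the initial decision (by the investigator) has been made to introduce Firmagon or GnRH agonist", so the physician has chosen the drug before the study begins.

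**Adjusted analyses.** Section 10.5.1, the primary analysis, estimates "the adjusted incidence rate ratio (IRR) of an incidence for patients on Firmagon as compared to GnRH agonist" by Poisson regression. The factors are age and stage for mortality, plus cardiovascular, diabetes or osteoporosis history for the matching adverse event of special interest (AESI). The rule for reading AESI risk uses the confidence interval of that ratio. Section 10.5.3 compares death and first AESI again by a Cox model "adjusted for potential confounding factors as described in Section 10.5.1". Sections 10.6.4 and 10.6.6 do likewise for serious cardiovascular events (CV SAE), with age, stage and prior cardiovascular disease.

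**Tests without these factors.**
- 10.5.2: time to death and "time-to first event of special interest, will be based on the log-rank test using the Kaplan-Meier methodology".
- 10.6.5: "Comparisons between the two treatment arms with respect to time-to first event of CV SAE will be based on the log-rank test", repeated with death included and in the subgroup with prior disease.
- 10.1.1: "The exact uniformly most powerful unbiased test of equal incidence rates will be used to flag significant differences between the two treatment groups". The table's stated aim is "To make a balanced comparison with respect to possible differences in drop-out rates".

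No strata, covariates or weights are named in these three sections, and none of the tests is labelled descriptive. Section 10.1 sets a two-sided 5% level for all safety tests.

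**The concern.** When the physician picks the drug, the arms may differ in age, stage and history. A crude log-rank or rate test then responds to that difference as well as to any drug effect, and its nominal 5% is not the error rate for a drug difference. The SAP accepts this for its models but still runs 5%-level tests of the same endpoints without the factors.

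Two consequences differ in weight.

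1. **General AE flags.** Dividing by person-years corrects for unequal follow-up, not for patient characteristics. No adjusted analysis of general AEs is planned, and section 2.1 makes identifying unrecognised adverse drug reactions a secondary objective. A flag produced by case mix, or a real excess hidden by it, would not be caught by another planned between-arm analysis.
2. **Log-rank tests.** Crude curves and p-values will stand beside adjusted rate and hazard ratios for the same endpoints. They may disagree, and 10.5.2 and 10.6.5 do not say which governs.

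**Working it through.** **The SAP's own figure.** Section 3.2 assumes 10% dropout over 5 years, uniform in time. Firmagon follow-up is therefore 1000 × (0.9 × 5 + 0.1 × 2.5) = 4,750 patient-years (PY), and 2,375 for 500 agonist patients. At 5.00 per 100 PY that is about 238 events, with an exact Poisson interval of 4.39 to 5.69. Table 2 gives 4.38 to 5.68. Every Table 2 limit is reproduced within 0.03, so these follow-up inputs are a fair base. The present point does not depend on Table 2.

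**Assumptions not in the SAP.** One binary risk factor, its prevalence in each arm, its risk ratio, and the death rate. The drug effect is null within risk strata.

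**Closed form for death.** Take 40% versus 30% metastatic, mortality ratio 4, and 8 deaths per 100 PY:
- Crude hazard ratio = (0.4 × 4 + 0.6) / (0.3 × 4 + 0.7) = 2.2 / 1.9 = 1.158.
- Deaths: 0.08 × 4,750 = 380 and 0.08 × 2,375 = 190.
- SE = √(1/380 + 1/190) = 0.089.
- Rejection = P(|Z + ln 1.158 / 0.089| > 1.96) = 38%.

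This is too high, because 4,750 and 2,375 PY assume that nobody leaves follow-up by dying. Simulating the same setting with 8 per 100 PY as the initial pooled hazard gave about 303 and 134 deaths on 3,939 and 2,017 PY. Then SE = √(1/303 + 1/134) = 0.104 and ln 1.158 / 0.104 = 1.41, which gives about 29%. Fewer deaths thus explain most of the gap. The simulated log-rank test, which also reflects depletion of high-risk patients, rejected in about 27–28% of runs.

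**Other simulated mortality settings (ratio 4).**
- 35% versus 30% metastatic: about 9–10%.
- 50% versus 30%: 76%.
- 40% versus 30% with 4 deaths per 100 PY: 19%.
- Balanced: 5.5%.
- Log-rank stratified on stage: 4.4–5.1% throughout.

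**Simulation at the SAP's cardiovascular rates** (5 and 10 per 100 PY, section 3.2). There were 1000 versus 500 patients, 5 years, 10% uniform dropout and 1,000 replicates (Monte Carlo SE about 0.7 points near 5%). The rate test is a conditional binomial test with doubled tails, close to the test in 10.1.1.

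| Factor, Firmagon vs agonist | Risk ratio | Rate per 100 PY | Crude log-rank | Exact rate test | Stratified log-rank |
|---|---|---|---|---|---|
| 30% vs 30% | 2 | 5 | 5.7% | 4.9% | 5.5% |
| 40% vs 30% | 2 | 5 | 7.0% | 6.1% | 4.2% |
| 40% vs 30% | 2 | 10 | 12.2% | 11.7% | 4.4% |
| 50% vs 30% | 2 | 5 | 21.8% | 20.9% | 4.3% |
| 50% vs 30% | 2 | 10 | 35.3% | 34.6% | 5.3% |
| 50% vs 30% | 3 | 10 | 69.8% | 69.1% | 6.4% |

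Separate runs of the second row gave about 9% for the log-rank test, so 7–9% is a fair range.

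**Main Treatment Period.** Section 10.4.1 counts AESIs only until the main treatment period ends. Adding censoring with an assumed mean of 3 years to that same setting lowered one run from 8.9% to 6.3%.

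**The case against.** The strongest reply is that the endpoints of 10.5.2 and 10.6.5 are already covered. Death and first AESI have an adjusted Poisson model and an adjusted Cox model; CV SAE has both, within a section labelled exploratory. The interpretation rule for AESI rests on the adjusted rate ratio, so no stated AESI conclusion turns on a log-rank p-value. Crude curves beside adjusted models are ordinary cohort reporting, and a divergence shows how much confounding is present. All of this stands. A reader might infer that the SAP compares death and AESI only by unadjusted tests; it does not.

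A reader might also infer that the p-values simply measure case mix, or that nothing at all is adjusted. The SAP supports neither. The tests would mix case mix with any drug effect, the SAP reports no imbalance, and 10.1.1 does allow for person-time. That the log-rank tests are unstratified is read from silence, though it is the natural reading.

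The large percentages come from assumed strong imbalance or a fourfold risk. Milder settings at cardiovascular rates give single digits, and rows with fewer events would show less. That stands too.

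On the remedy, two age groups by four stages by two history levels make 16 strata, and a stratified rate ratio for every preferred term would be very sparse. This is a fair limit on the fix. The reply has no answer for the general AE flags, which have no adjusted version, or for 5% tests left without a descriptive label.

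**Conclusion.** The point holds, as a correction the SAP should make rather than a flaw in its primary analysis. The AE flags and the log-rank tests are 5%-level between-arm comparisons that leave out factors the SAP itself treats as potential confounders.

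It is strongest for the AE flags. For death, AESI and CV SAE, the risk is a p-value that conflicts with the adjusted result without displacing it.

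With no drug effect, crude log-rank rejection is about 27–28% for 40% versus 30% metastatic with mortality ratio 4 and 8 initial deaths per 100 PY. It is about 9–10% for 35% versus 30%. It is about 7–9% for 40% versus 30% with risk ratio 2 at 5 events per 100 PY, and less if only main-treatment-period events count. The 38% from the closed form should not be quoted. All these sizes rest on assumed prevalences and risk ratios. Imbalance in the other direction could hide a real excess on Firmagon.

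**What to change.** 1. **10.5.2 and 10.6.5.** Either stratify the log-rank tests by the 10.5.1 factors (age group and stage, plus the relevant history where strata are not too sparse), or show crude Kaplan-Meier curves as descriptive, without p-values. Standardised or weighted curves are optional.
2. **Precedence.** State that the adjusted Poisson and Cox models govern inference on death, AESI and CV SAE if a log-rank result disagrees.
3. **10.1.1.** For terms with enough events, for example the common AEs already defined in 10.3.2 as at least 5% of patients, base the flag on an age- and stage-stratified Mantel-Haenszel rate ratio with 95% CI. Label crude flags for rarer terms as descriptive screening only.

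The cost is SAP wording, standard programming options and a slight loss of power from sparse strata. The factors are already specified for the primary model. Stratification removes bias from those factors only; unmeasured differences, and differences within broad categories, remain.

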### **10.5.3 Cox Proportional Hazards Model**

Hazard ratios between Firmagon and GnRH agonist (=reference) with respect to death, and (first) event of special interest will be estimated based on the Cox proportional hazard model, adjusted for potential confounding factors as described in Section 10.5.1. Model parameters will be deemed statistically significant assuming a two-sided alpha level of 0.05 based on Wald test for individual parameters.

## 10.6 Exploratory Cardiovascular Analyses

This section addresses explorative cardiovascular events, defined as Major Adverse Cardiovascular Event (MACE). Analysis will be performed both in the *overall* patient population (Safety Analysis Set), as well as in the *CVD* subgroup, i.e. patients with at least one prior CV event reported in their medical history that was within the *broad* scope search term of any of the five SMQs:

- Myocardial infarction
- Ischaemic cerebrovascular conditions
- Haemorrhagic cerebrovascular conditions
- Embolic and thrombotic events, arterial
- Other ischaemic heart disease

The time to first event for any SAE within the *narrow* scope the five SMQs listed above is defined as the '*time to CV SAE*'. In addition, a combined endpoint defined as '*time to CV SAE or death from any cause*' will be analysed. Note that death itself is not an adverse event, but it may be an outcome of an adverse event.

### 10.6.1 Overview of Treatment-Emergent Adverse Events Classified as a CV SAE

Summary table to be presented as defined in Section 10.4.3. This table will be presented for both overall and subgroup of patients with CVD at baseline.

### 10.6.2 Overview of Treatment-Emergent Adverse Events Classified as a CV SAE or Adverse Events Leading to Death

Summary table to be presented as defined in Section 10.4.3. This table will be presented for both overall and subgroup of patients with CVD at baseline.

### 10.6.3 Incidence of Adverse Events Classified as a CV SAE

Summary tables will be prepared for the incidence of the treatment-emergent adverse events classified as a CV SAE. The tables will be sorted by

- MedDRA SOC (alphabetically) and PT (in decreasing frequency of occurrence)
- MedDRA SMQ (in decreasing frequency of occurrence) and PT (in decreasing frequency of occurrence).

Tables will be prepared for both overall and subgroup of patients with CVD at baseline.

#### **10.6.4 Incidence of Adverse Events Estimated with Poisson Regression Model**

The primary analysis of Section 10.5.1 will be repeated for the CV SAE. This analysis will be repeated for the CV SAE including death as endpoint, and in the subgroup of patients with prior CVD at baseline. In all, four analyses are planned.

The estimated hazard ratios will (at a minimum) be adjusted for age, stage of prostate cancer and prior CVD (in overall population).

#### **10.6.5 Time-to-First Event by Kaplan-Meier Methodology**

Comparisons between the two treatment arms with respect to time-to first event of CV SAE will be based on the log-rank test using the Kaplan-Meier methodology. This analysis will be repeated for the CV SAE including death as endpoint, and in the subgroup of patients with prior CVD at baseline. In all, four analyses are planned.

#### **10.6.6 Cox Proportional Hazards Model**

Hazard ratios between Firmagon and GnRH agonist (=reference) with respect to CV SAE will be estimated using the Cox proportional hazard model. Model parameters will be deemed statistically significant assuming a two-sided alpha level of 0.05 based on Wald test for individual parameters.

This analysis will be repeated for the CV SAE including death as endpoint, and in the subgroup of patients with prior CVD at baseline. In all, four analyses are planned.

The estimated hazard ratios will (at a minimum) be adjusted for age, stage of prostate cancer and prior CVD (in overall population) as defined by SMQ terminology.

## **10.7 Safety Laboratory Variables**

There is no planned collection of safety laboratory variables in the study.

## **10.8 Prostate Cancer Variables**

The following variables may be obtained at follow-up visits and will be presented if so.

### **10.8.1 Change in Prostate Cancer Stage**

Change in stage of prostate cancer since last visit is monitored at each follow-up visit, and the outcome is “yes” or “no”. If not performed, “no” change in prostate cancer will be assumed. For each visit, the number of patients with a confirmed change (“yes”) will be tabulated for each treatment arm.

Listings will present the specific change as recorded by the investigator.

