#### Secondary Objectives

The secondary objectives of this Observational study are to:

- Compare the relative risks of the AESI in those patients treated with Firmagon and those treated with a GnRH agonist
- Identify any new potentially unrecognized adverse drug reactions (ADRs) by collecting adverse events (AEs) in this population
- Describe the long-term clinical evolution of PCa in patients treated with Firmagon
- Describe the all-cause mortality in patients treated with Firmagon

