### 7.3 History and Stage of Prostate Cancer

A summary table of history and stage of PCa will be presented, containing the following information:

- number of patients diagnosed with PCa
- previous cancer therapies (Radical Prostatectomy, Radiotherapy Neoadjuvant/Adjuvant Hormonal Therapy, and Other)
- ECOG (Eastern Cooperative Oncology Group) performance status, a score in the range of 0 (=fully active) to 4 (=completely disabled)
- Pathological stages of primary tumor (pT) and regional lymph node (pN) (for patients having undergone radical prostatectomy only) (as defined below)
- Gleason score (as defined below)
- stage of prostate cancer (TNM classifications) (as defined below)
- PSA baseline category (as defined below)

The following pathological stages will be recorded and summarized by treatment group:

pT (primary tumor)

- Not done
- Not applicable
- PT2
- PT3MR-
- PT3MR+

pN (regional lymph node)

- Not done
- Not applicable
- PN0
- PN1
- PN2/3

The Gleason score is calculated as the sum of the Gleason grade of the primary and secondary patterns. The following categories will be presented:

- 2-4
- 5-6
- 7-10

The stage of prostate cancer, based on the TNM classification, includes the following categories:

- Localised: T1/2 & (NX or N0) & M0,
- Locally Advanced: [T3/4 & (NX or N0) & M0], or [N1 & M0],
- Metastatic: M1
- Not classifiable: Results from T, N, and M categories that could not be resolved to Localised, Locally Advanced, or Metastatic

The following baseline PSA categories will be used:

- [0-10] ng/mL
- ]10-20] ng/mL
- ]20-50] ng/mL
- ]50- ] ng/mL

Dates of diagnosis, and start (and stop) of previous therapies will be presented in patient listings.

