### **10.8.3 T-Score**

The number of patients (and percentage) in each category accordingly to [Table 3](#) will be tabulated by treatment group and visit.

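### The stage-change table in SAP 10.8.1 counts any change since the last visit, without direction, denominator or cumulation, so it cannot summarise prostate cancer progression

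*SAP*

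**What the plan says.** One secondary objective in SAP 2.1 is: "Describe the long-term clinical evolution of PCa in patients treated with Firmagon". Stage is summarised at baseline under SAP 7.3: "The stage of prostate cancer, based on the TNM classification, includes the following categories", namely Localised, Locally Advanced, Metastatic and a residual class, "Not classifiable: Results from T, N, and M categories that could not be resolved to Localised, Locally Advanced, or Metastatic".

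For follow-up, SAP 10.8 opens with "The following variables may be obtained at follow-up visits and will be presented if so". SAP 10.8.1 then says "Change in stage of prostate cancer since last visit is monitored at each follow-up visit, and the outcome is" yes or no. If stage was not assessed, no "change in prostate cancer will be assumed. For each visit, the number of patients with a confirmed change" is tabulated for each arm. The detail is kept elsewhere: "Listings will present the specific change as recorded by the investigator".

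The neighbouring T-score table in SAP 10.8.3 is specified differently, by category and with percentages: "The number of patients (and percentage) in each category accordingly to" Table 3.

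The other summary of the course of the cancer is PSA, described by median and inter-quartile range at each visit (SAP 9.1.6). The Kaplan-Meier and Cox analyses in SAP 10.5 and 10.6 cover death, events of special interest and serious cardiovascular events. None covers progression of the cancer.

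**The concern.** The table reduces an ordered, directional variable to a bare count of any change. Three features keep it from describing disease evolution.

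- **Direction.** A move from M0 to M1, a fall in category, and a first scan that resolves MX to M0 can each be entered as yes. Nothing in 10.8.1 separates them, and it does not say whether stage means the 7.3 category or any T, N or M component.
- **Denominator.** Only a number of patients is planned. The arms differ in size by design, and staging is optional at every visit.
- **Cumulation.** Each entry looks back only to the previous visit. The table does not show how many different patients ever changed, or when each first did.

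A report that followed the plan exactly would cover up to five years of follow-up and contain no summary of how many Firmagon patients moved to a worse stage, or when. A reader would have to reconstruct this from patient listings.

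**Working it through.** The SAP states no figure for stage change, so there is none to reproduce. The check is to ask what the planned table would leave undetermined. The visit schedule and arm sizes come from the SAP; the counts and rates are assumptions chosen for illustration.

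**Inputs from the SAP**
- Follow-up every 3 months for 2 years, then every 6 months for 3 years (3.1): 24/3 + 36/6 = 8 + 6 = 14 follow-up points.
- Arms of about 1000 (Firmagon) and 500 (GnRH agonist) (section 3).
- Unassessed stage counted as no change (10.8.1).

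**1. Patients and direction.** Assume 10 yes entries per visit in the Firmagon arm. The table then holds 14 × 10 = 140 entries.
- Fewest patients: the same 10 at every visit, 10/1000 = 1.0%.
- Most patients: all different, 140/1000 = 14.0%.
- Progressions among the 140 entries: anything from 0 to 140, because direction is not tabulated.

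**2. Comparing the arms.** The same 10 entries at a visit are 10/1000 = 1.0% of one arm and 10/500 = 2.0% of the other. A bare count hides this twofold difference.

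**3. Interval length.** Assume a constant monthly rate λ and a fixed number at risk. The expected proportion changing is 1 − exp(−3λ) over 3 months and 1 − exp(−6λ) over 6 months. Their ratio is 1 + exp(−3λ), which is close to 2 when the rate is low. With 2% changing per 3 months it is 1 + 0.98 = 1.98. The count per visit would therefore almost double after year 2 with no change in the disease.

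**4. Unassessed counted as no.** Assume 2% of 1000 patients truly change in an interval, and that being staged is unrelated to changing.

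| Share of patients staged | Tabulated count per 1000 |
|---|---|
| 100% | 1000 × 0.02 × 1.00 = 20 |
| 75% | 1000 × 0.02 × 0.75 = 15 |
| 50% | 1000 × 0.02 × 0.50 = 10 |
| 25% | 1000 × 0.02 × 0.25 = 5 |

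A change missed in one interval may be entered at a later staging, so part of this effect is delay rather than loss. The table could not show which.

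**The case against.** The strongest reply is that 10.8.1 does not claim to measure progression. SAP 2.2 lists PSA among the endpoints but not stage change. SAP 10.8 presents these variables only as they happen to be obtained, and the objective is descriptive and concerns Firmagon patients only. The specific change is in the listings, by-visit attendance is tabulated under section 4, and mortality is analysed fully. The layout may also be refined in the separate tables, listings and figures specification (section 14), and what the case report form accepts as a confirmed change is not shown.

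Much of this stands as a limit on the point. Direction is not lost from the data; the weakness is in the planned summary. No figure in the SAP is wrong, and the near-doubling after year 2 would be evident to a reader who knows the schedule. What does not stand is that the objective is served anyway. Attendance is not the same as being staged, all-cause mortality is a separate objective, and listings for about 1500 patients do not replace a summary.

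A reader might also infer that patients metastatic at baseline cannot worsen and so dilute the result, understating progression by a calculable factor. The SAP does not support this. Section 10.8.1 plans a number, not a proportion over all patients, and tabulates no stable group. Appendix 2 has M1a, M1b and M1c, so a change may be recorded in a patient who is already M1. The SAP gives neither the share of patients metastatic at baseline nor the share of entries that are reclassification, so no inflation or dilution factor can be derived from it.

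**Conclusion.** The point holds as a weakness in the planned summary. The 10.8.1 table pools directions, gives no denominator and is not cumulated, so neither the frequency nor the timing of progression can be read from it. Only descriptive PSA otherwise speaks to the course of the cancer.

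The size cannot be fixed from the SAP. In the illustration, one and the same table is compatible with 1.0% to 14.0% of Firmagon patients ever changing, and with none or all of the entries being progressions. This rests on an assumed 10 entries per visit, 14 nominal follow-up points and the full planned arm of 1000. The near-doubling after year 2 rests on a constant rate and a fixed number at risk.

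It would go too far to say that the study cannot describe progression at all. The specific change is recorded, so a proper summary can be derived. This is a cheap improvement to a descriptive secondary objective and does not affect the primary analyses.

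**What to change.** Amend 10.8.1 as follows, using the specific change already recorded by investigators.

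1. State what counts as a change, and map each one to the 7.3 categories.
2. For each visit interval and arm, tabulate separately: moves to a higher category (Localised to Locally Advanced or Metastatic; Locally Advanced to Metastatic); moves to a lower category; changes to or from Not classifiable; and new M1 sub-sites in patients already metastatic.
3. Give each as n/N, where N is the patients with stage assessed in that interval. Show unassessed patients on their own line and do not count them as unchanged.
4. Report the cumulative incidence of the first recorded move to a higher category among patients with a known non-metastatic stage at entry, with death as a competing event. State the time origin, for example the start of the Main Treatment Period in 8.1. The objective needs this for Firmagon; the comparator can be shown descriptively.
5. Use the recorded entry stage for this purpose even where section 7 would set baseline information to missing for Firmagon patients already on treatment. Otherwise the at-risk set is undefined for those patients, in one arm only.
6. State that staging is done at the physician's discretion, so the curve shows recorded progression and its timing depends on when staging took place.

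The cost is SAP wording, some coding of the recorded changes and a smaller denominator. No new data collection is needed.
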